### **II. Clinical assessment of chemotherapy induced mucositis**

- Mucositis will be assessed at baseline and by the end of every two chemotherapy cycles through the use of common terminology criteria for adverse events "CTCAE, version 5.00, 2017" (17).

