**- The primary and secondary endpoints:**

The primary endpoint is the percentage of patients with peripheral sensory neuropathy grade  $\geq 2$ , the variation of 12-item neurotoxicity questionnaire (Ntx-12) total score and the variation in grades of mucositis. The secondary endpoint is the change in the serum concentrations of the measured biological markers.

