**- Sample size calculation:**

According to the results of previous studies, the total number of subjects required to detect the effect of neuro-protective drugs in patients received neuro-toxic chemotherapy was 41 patients with 5% significance, 80% statistical power and an attrition of 15 % (19, 20). In this context, during the current study, a total sample size of 41 patients in both arms will be sufficient to detect the effect. Assuming that the attrition rate will be 15 %, the initial sample size will be 48 patients in both arms with 24 patients in each arm.

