**- Statistical analysis:**

- The collected data will be tabulated using Microsoft® Office Excel, 2019 (Microsoft Corporation).
- The statistical analysis will be carried out using SPSS statistical package version 26.0 (IBM corporation software group, USA).
- Data will be tested for normality using Shapiro-Wilk test or Kolmogorov–Smirnov test.
- Parametric data will be analyzed using Paired and un-Paired *t*-test to compare the means within the same group and to compare the means of the two groups respectively.
- Non- Parametric data will be analyzed using Mann Whitney U test to compare the means within the same group and to compare the means between groups.
- Categorical data will be analyzed using Chi-Square test.
- Fisher’s exact test will be used to analyses the reported adverse effects.
- Correlation between variables will be assessed using Pearson or Spearman correlation coefficient which appropriate.
- Data will be expressed as the mean  $\pm$  SD, medians, range, number and percent as appropriate.
- The significance level will be set at  $p \leq 0.05$ .

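### Mucositis grade is an ordered primary-endpoint component with no test assigned to it; the likely reading (chi-square) and the adverse-effect reading (Fisher's exact) both ignore the order

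*Combined protocol and SAP*

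**What the plan says.** The endpoints section lists three components of the primary endpoint, and the third is "the variation in grades of mucositis". It gives no time point and no rule for reducing a patient's grades to one value. Section C.II supplies the scale (CTCAE version 5) and the schedule: "Mucositis will be assessed at baseline and by the end of every two chemotherapy cycles". With 12 cycles planned, that is 12 / 2 = 6 post-baseline grades per patient.

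Three rules in the Statistical analysis section could cover these grades:

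- Categorical data: "Categorical data will be analyzed using Chi-Square test".
- Data that are not parametric (the quote starts after the bullet's prefix Non-): "Parametric data will be analyzed using Mann Whitney U test to compare the means within the same group". The same sentence extends the test to comparisons between groups.
- Adverse effects: Fisher's "exact test will be used to analyses the reported adverse effects". Section D grades adverse effects with the same CTCAE version that section C.II uses for mucositis.

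None of these rules mentions mucositis or toxicity grades.

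**The concern.** Pearson's chi-square on a 2 x k table of arm by grade treats the grades as unordered labels. Shuffling the grade columns leaves its p-value unchanged, and it spreads its sensitivity over k - 1 degrees of freedom. The stated aim is protection, which means milder grades on pentoxifylline. A test that uses the order is directed at that question.

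Chi-square is the likely reading for two reasons. Grades are naturally shown as counts and percentages. The Mann-Whitney bullet follows the normality check and speaks of comparing means, which suggests continuous measurements that fail that check.

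Two things are at stake. In a trial this small, a real shift toward milder mucositis is more likely to be missed. And because three tests are open for a primary component, the choice could be made after the results are seen.

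**Working it through.** **Sample size in the plan.** The plan states "a total sample size of 41 patients in both arms will be sufficient to detect the effect", and then "the initial sample size will be 48 patients in both arms with 24 patients in each arm". Check: 41 x 1.15 = 47.2, rounded up to 48; dividing instead, 41 / 0.85 = 48.2. The step from 41 to 48 reproduces. The 41 cannot be recomputed, because no effect size, SD or event rate is given. The evaluable number per arm is 24 x 0.85 = 20.4, so about 20.

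**Inputs from the plan.** Significance level and attrition come from "with 5% significance, 80% statistical power and an attrition of 15". A two-sided test is assumed, since the plan does not say. The number per arm is 20 (after attrition) or 24 (none lost).

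**Assumed inputs.** The grade distribution, the number of grades in use and the treatment effect are not in the documents, so a range is shown.

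**Effect model.** A uniform (proportional-odds) shift multiplies each cumulative odds of a milder grade by the odds ratio (OR). Example with control grades 0 to 3 at 20/30/30/20% and OR 3:

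- Control cumulative probabilities: 0.20, 0.50, 0.80; odds 0.25, 1, 4.
- Times 3: 0.75, 3, 12; cumulative probabilities 0.429, 0.750, 0.923.
- Treated distribution: 42.9/32.1/17.3/7.7%.

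**Tests compared.**

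- Chi-square: X² = sum of (O - E)²/E, with degrees of freedom equal to non-empty grades minus 1.
- Mann-Whitney, tie-corrected: z = [W - n(N+1)/2] / sqrt{(n²/12)[(N+1) - sum(t³ - t)/(N(N-1))]}, where N = 2n, W is the rank sum in one arm and t is the number of patients at each grade.

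**Simulated power, 20 per arm** (20,000 trials per scenario; 8,000 for the row in whole percents):

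| Control distribution (%) | OR 3: chi-square / rank | Gain | OR 4: chi-square / rank | Gain |
|---|---|---|---|---|
| 2 levels, 50/50 | 37.6 / 37.6 | 0 | 52.8 / 52.8 | 0 |
| 3 grades, 50/30/20 | 29.7 / 39.4 | 10 | 41.2 / 53.5 | 12 |
| 4 grades, 20/30/30/20 | 29.6 / 45.9 | 16 | 46.3 / 65.2 | 19 |
| 4 grades, 30/35/25/10 | 27 / 44 | 17 | 43 / 63 | 20 |
| 5 grades, 20 each | 26.7 / 47.2 | 20 | 41.6 / 65.9 | 24 |
| 5 grades, 20/30/30/15/5 | 25.2 / 46.6 | 21 | 39.6 / 64.9 | 25 |

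At OR 2 the gain is smaller: about 8 points with four grades (13.7% against 22.1%) and about 5 with three. At 24 per arm with control 20/30/30/20%, power goes from 36.1% to 53.5% at OR 3 and from 55.4% to 73.1% at OR 4.

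**Analytic check.** A 1-df test with 80% power has noncentrality (1.960 + 0.842)² = 7.85. The same noncentrality on 2, 3 and 4 df gives 70.9%, 64.5% and 59.5%, a loss of about 9, 16 and 21 points. This agrees with the pattern for three, four and five grades.

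**When the shift is not uniform.** Take control 20/30/30/20% against treated 20/60/20/0%, where the benefit is mainly the removal of severe grades. At 20 per arm chi-square has 52.2% and Mann-Whitney 37.6%; at 24 per arm, 65.1% and 43.5%. The ranking of the tests reverses.

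**Sparse cells.** In the OR 3 example the expected count in the worst grade is 20 x (0.200 + 0.077)/2 = 2.8 per arm. About 99% of the four-grade tables at 20 per arm had at least one expected count below 5. Type I error nevertheless stayed at about 4 to 5% for both tests, so lost power is the main issue, not false positives.

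**The case against.** The strongest reply is that the plan never sends mucositis grade to chi-square. A reader might infer that it does, because chi-square is the only test named for categorical data. The documents do not support that as a stated commitment. Mann-Whitney is listed for comparisons between groups, medians and ranges are among the planned summaries, and the endpoint is worded as variation from a schedule that includes baseline. A change-in-grade score could fairly be treated as non-normal numeric data and go to the rank test. This stands: chi-square is the likely reading, not an assignment.

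A reader might also take 17 to 20 points as the power that this trial loses. That figure needs four grades in use, a uniform shift and an odds ratio of 3 to 4, none of which the documents give. Other plausible inputs yield smaller, larger, zero or reversed differences. This stands too. The reversed example is not an odd pattern, since its treated patients are no worse at any cut of the scale.

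Two lesser replies also hold. Fisher's exact test would deal with the small expected counts, though it would still ignore the order. And the direction of a significant chi-square can be read from the reported percentages, although the test itself does not assess it.

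None of this removes the gap. Two of the three available readings discard the order, and the plan does not choose among them for a primary component.

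**Conclusion.** The point holds in a limited form. The plan leaves the test for an ordered primary component open, and the likely reading and the adverse-effect reading both ignore the order.

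If chi-square is used, the cost against a rank test is roughly 5 to 25 points of power at about 20 per arm. This assumes a uniform shift toward milder grades, three to five grades in use and odds ratios of about 2 to 5. The cost is zero with two levels. It can turn into a gain for chi-square when the benefit is concentrated at one end of the scale.

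It would be wrong to infer that changing the test rescues this endpoint. At 20 per arm and odds ratios of 3 to 4, the rank test reaches only about 39 to 66% in the scenarios with three or more grades. The sample size section is argued from neuro-protective drugs and gives no mucositis effect.

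The change is worth making because it fits the protective aim, closes an open choice and costs almost nothing.

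**What to change.** In the Statistical analysis section, add a sentence or two for mucositis that:

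1. defines one value per patient, for example the worst of the six post-baseline grades, and says how missed assessments are handled;
2. compares the arms with a tie-corrected Mann-Whitney test;
3. reports a proportional-odds odds ratio with its 95% confidence interval, next to the count and percentage at each grade;
4. keeps chi-square or Fisher's exact test for binary and unordered variables.

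The cost is wording only. No patients, visits or data are added, and Mann-Whitney is already in the plan. The drawback is less sensitivity to differences that are not a uniform shift, such as an effect confined to severe grades; the grade-by-grade table would keep such a pattern visible. The text should be settled before any comparison of outcomes by arm.

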## **D. Assessment of participants' adherence, side effects and tolerability**

Pentoxifylline will be provided on biweekly basis and the participants' adherence will be assessed through counting the returned tablets. Participants will be followed-up by weekly telephone calls and direct meetings during chemotherapy cycles to assess their adherence and to report any drug related adverse effects. The adverse effects will be collected and graded according to the National Cancer Institute Common Terminology Criteria for Adverse events "NCI-CTCAE; version 5, 2017" (17). Participants will be considered non-adherent and excluded from the study if not consumed the provided tablets or lost the follow-up meeting at any time of intervention or changed regimen.

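### Adverse effects get counts and a Fisher p-value but no risk difference with interval, so the planned output does not show how much excess harm 20–24 patients per arm can exclude

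*Combined protocol and SAP*

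**What the plan says.** Section D of the Measurements is headed "Assessment of participants' adherence, side effects and tolerability". It provides for weekly telephone calls and for meetings during the cycles, and states: "The adverse effects will be collected and graded according to the National Cancer Institute Common Terminology Criteria for Adverse events" (version 5). The same section removes from the study participants who do not take their tablets, miss a follow-up meeting or change regimen.

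For the analysis, the Statistical analysis section says that Fisher's "exact test will be used to analyses the reported adverse effects". "The significance level will be set at" p ≤ 0.05, with no statement of whether tests are one- or two-sided. A general line adds that data will be expressed as number and percent where appropriate. No risk difference, confidence interval or margin is given for adverse effects.

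The Sample size calculation refers to earlier studies of neuro-protective drugs with "5% significance, 80% statistical power and an attrition of 15" per cent, and concludes that "a total sample size of 41 patients in both arms will be sufficient to detect the effect". After allowing for attrition, "the initial sample size will be 48 patients in both arms with 24 patients in each arm". Nothing in that section concerns adverse effects.

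**The concern.** Pentoxifylline is added to chemotherapy to prevent toxicity, so its value depends on weighing benefit against any harm that it adds. The protocol plans to look at that harm, but the only formal comparison it names is a test that ends in significant or not significant. At this size such a test will often be non-significant when a sizeable excess exists. The same p > 0.05 can come from data that limit the excess to under 20 points or from data that allow an excess of about 45 points, and the p-value does not tell the two apart. If no interval is planned, the report may carry only a line of non-significant p-values beside the counts, and readers will have to work out for themselves what has been excluded.

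**Working it through.** **Inputs from the documents.** 48 randomised, 24 per arm; 41 after attrition of 15% (Sample size calculation). Fisher's exact test at p ≤ 0.05 (Statistical analysis).

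**Assumptions, not in the documents.** A two-sided test; a true excess of 20 percentage points on pentoxifylline; a placebo rate p between 0% and 40%. The protocol does not say how 41 would split, so 20/20, 20/21, 21/20 and 24/24 (placebo/pentoxifylline) are all shown.

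**The plan's own figure.** 41 × 1.15 = 47.15, rounded up to 48; 41 / 0.85 = 48.2, rounded up to 49. The stated 48 is reproduced by the first and is within one patient of the second. The base figure of 41 cannot be re-derived, because no effect size, rate or SD is given. No power for adverse effects is stated, so there is none to reproduce.

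**Miss rate.** For arms of size a (placebo) and b (pentoxifylline), with X ~ Bin(a, p) and Y ~ Bin(b, p + 0.20):

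miss = 1 − Σ P(X = x) · P(Y = y), summed over all tables (x, y) with two-sided Fisher p ≤ 0.05.

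| Placebo vs pentoxifylline | 24/24 | 20/21 | 21/20 | 20/20 |
|---|---|---|---|---|
| 0% vs 20% | 46.0% | 58.6% | 41.1% | 63.0% |
| 5% vs 25% | 60.3% | 66.5% | 56.9% | 70.1% |
| 10% vs 30% | 68.6% | 72.5% | 66.4% | 75.8% |
| 15% vs 35% | 73.2% | 76.3% | 72.0% | 79.1% |
| 20% vs 40% | 76.4% | 78.8% | 75.9% | 80.8% |
| 30% vs 50% | 78.6% | 81.8% | 80.6% | 83.7% |
| 40% vs 60% | 78.5% | 82.0% | 82.0% | 85.7% |

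For placebo rates of 5–20% the range is 56.9–80.8%. For 0–40% it is 41.1–85.7%. With a one-sided test at 0.05, over placebo rates of 0–40%, the miss rate is 46–69% at 24/24 and 62–78% at 20/20.

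**Events needed for significance (placebo vs pentoxifylline).** At 24/24, 20/21 and 20/20: 0 vs 5, 1 vs 7, 2 vs 9 or 3 vs 10. At 21/20: 0 vs 4, 1 vs 6, 2 vs 8 or 3 vs 9.

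**Excess needed for 80% power (placebo rates 0–30%).** 27–43 points at 24 per arm and 32–48 points at 20 per arm.

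**What an interval adds.** The Newcombe interval combines the Wilson limits (l, u) of each arm, with subscript 1 for placebo, 2 for pentoxifylline and d = p₂ − p₁:

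lower = d − √[(p₂ − l₂)² + (u₁ − p₁)²]; upper = d + √[(u₂ − p₂)² + (p₁ − l₁)²].

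Worked case, 1/20 vs 6/21: p₁ = 0.050 (Wilson 0.009 to 0.236), p₂ = 0.286 (0.138 to 0.500), d = 0.236.
- Lower: 0.236 − √(0.148² + 0.186²) = −0.002.
- Upper: 0.236 + √(0.214² + 0.041²) = 0.453.
- Fisher p = 0.093.

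| Placebo vs pentoxifylline | Fisher p | Risk difference (95% Newcombe), points |
|---|---|---|
| 2/24 vs 2/24 | 1.00 | 0 (−19 to +19) |
| 2/24 vs 6/24 | 0.24 | +17 (−5 to +37) |
| 1/20 vs 6/21 | 0.093 | +24 (−0.2 to +45) |
| 2/24 vs 8/24 | 0.072 | +25 (+1.7 to +46) |

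All four results are non-significant. The upper limits run from 19 to 46 points. Even no events in 24 patients leaves a two-sided 95% upper limit of 1 − 0.025^(1/24) = 14%.

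**The case against.** **No faulty inference has been written down.** A reader might infer that the protocol will treat p > 0.05 as proof of tolerability. It does not say so. Tolerability is not among the primary or secondary endpoints, and the stated aim is protection against neuropathy and mucositis. This stands: the point concerns a missing estimate and a missing safeguard, not an error already made.

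**Fisher's test is not the only output.** Number and percent are planned too, so 1 of 20 against 6 of 21 would be visible, and anyone could compute the difference and an interval from published counts. This stands as far as it goes. Fisher's test is the only inferential comparison, not the only information. But a precision statement should be in the plan, not left to the reader.

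**The miss rates rest on chosen inputs.** The documents give no placebo rate, no excess of concern and no sidedness. This stands, and is why the range is tied to its assumptions and shown across splits of 41. If an effect is absent on placebo, the miss rate can fall to 41%.

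**Low power for harm is usual in a trial of 48, and Fisher's test suits sparse counts.** Both are true. Neither the test nor the sample size is faulted here. Low power is the reason to report an interval.

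**Newcombe intervals and Fisher p-values can disagree.** 2/24 vs 8/24 shows it: p = 0.072, yet the interval excludes zero. Naming one interval method in advance and calling the p-value descriptive deals with this.

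**Conclusion.** The point holds as a minor one. The only inferential comparison planned for adverse effects is a Fisher test at p ≤ 0.05, in a trial sized for efficacy alone. With 20–24 patients per arm and a two-sided test, a true 20-point excess would be missed about 57–81% of the time for assumed placebo rates of 5–20%, and about 41–86% over 0–40%. A non-significant p-value therefore cannot by itself show how much harm the data exclude. The gap is the lack of a risk difference with its interval, and of a sentence on how non-significance will be read. The documents do not support the stronger reading that the test is wrong or that the plan equates non-significance with tolerability. The missing interval and sentence follow from the text alone; the size of the miss rate depends on the assumed rates and sidedness.

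**What to change.** Replace the Fisher bullet in the Statistical analysis section with wording such as:

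*For any adverse effect, any adverse effect of grade 3 or higher, and each reported term, the number and percentage of patients per arm and the risk difference (pentoxifylline minus placebo) with a 95% Newcombe interval will be given. The denominator is all randomised patients who took at least one tablet, including those later excluded for non-adherence, a missed follow-up meeting or a changed regimen. Fisher's exact p-values are descriptive. A p-value above 0.05 will not be taken as evidence of tolerability, and any statement on tolerability will quote the upper confidence limit.*

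The denominator matters because the exclusion rule in section D could remove patients who stopped their tablets because of an adverse effect.

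The cost is a few sentences and some extra table columns, computed from counts already collected, with no added patients or visits; events recorded before a patient is excluded must be kept. The downsides are that the intervals will be wide, that they may occasionally disagree with Fisher's p-value, and that any tolerability claim will be more modest.

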### **B. Blood sample collection and biochemical assessment**

Before starting the first chemotherapy cycle (baseline) and after the last chemotherapy cycle, 5 ml of venous blood will be withdrawn by antecubital venipuncture from each participant between 8:30 and 10:30 am into plain test tube and centrifuged at 3000 rpm for 10 min. The separated sera will be frozen at  $-80^{\circ}\text{C}$  until analysis of the biological parameters which include:

- Malondialdehyde (MDA) as oxidative stress marker (colorimetry).
- Tumor necrosis factor alfa (TNF- $\alpha$ ) as pro inflammatory marker (ELISA).
- Neurotensin (NT) as a potential marker for neuropathic pain (ELISA).
- Citrulline as a biomarker for mucositis (ELISA).

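### The planned correlations leave pairs, time point and treatment arm undefined; if the arms are pooled, a treatment effect on both variables can by itself create a correlation

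*Combined protocol and SAP*

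**What the plan says.** The Statistical analysis section gives this analysis one line: "Correlation between variables will be assessed using Pearson or Spearman correlation coefficient which appropriate". It does not state which variables are paired, whether baseline values, final values or changes are used, or whether the two arms are analysed together. No partial correlation, regression or by-arm correlation appears elsewhere in the protocol. The threshold in the same list ("The significance level will be set at" p ≤ 0.05) is not restricted to the endpoints, so it covers the correlations too.

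The endpoints section makes neuropathy of grade 2 or more, the Ntx-12 score and mucositis grade primary, and the changes in serum markers secondary. The section on blood samples ties two of the four markers to a clinical outcome: "Neurotensin (NT) as a potential marker for neuropathic pain (ELISA") and "Citrulline as a biomarker for mucositis (ELISA"). Markers are measured only at baseline and after the last cycle. The clinical measures are taken at baseline and after every two cycles.

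**The concern.** The trial is built on the expectation that the drug moves both the markers and the clinical scores. Treatment arm is then a potential common cause of the two variables in any marker-outcome pair. In a correlation over all patients, the treated patients lie towards one corner of the scatter plot and the controls towards the other. That separation gives a non-zero coefficient even if, within each arm, the marker says nothing about the patient's symptoms. The better the drug works on both variables, the larger this artefact becomes.

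At stake is any statement that neurotensin tracks neuropathic pain, that citrulline tracks mucositis, or that the oxidative and inflammatory pathway described in the Introduction explains the clinical result. Correlation is the only listed analysis that relates one patient's marker to that patient's outcome, so such statements would rest on it.

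**Working it through.** **Inputs from the protocol.** The Sample size section says that "a total sample size of 41 patients in both arms will be sufficient to detect the effect", and that "the initial sample size will be 48 patients in both arms with 24 patients in each arm", with 15% attrition and 80% power. The significance level is 5%, taken here as two-sided because the protocol does not say.

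**The plan's own figure.** 41 / (1 − 0.15) = 48.2 and 41 × 1.15 = 47.15, so the stated 48 is reproduced to within a patient. The 41 cannot be rebuilt, because no effect size, SD or event rate is given. The protocol states no figure for the correlation analysis.

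**Assumed effect sizes.** As an anchor, a comparison of two means with 41 / 2 = 20.5 patients per arm has 80% power for a standardised difference of (1.960 + 0.842) × √(2 / 20.5) = 0.875 SD by the normal approximation, or about 0.9 SD by the t-test. This is back-calculated, not stated in the protocol, so a range around it is shown.

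**Expected pooled correlation.** Let the two variables be independent within each arm, with treatment shifts d1 and d2 in SD units. With q = n1 × n2 / N², the correlation over all patients is

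ρ = d1 × d2 × q / √[(1 + d1² q)(1 + d2² q)].

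For 21 + 20 patients, q = 420 / 1681 = 0.250. With d1 = d2 = 0.875, d² q = 0.766 × 0.250 = 0.191 and ρ = 0.191 / 1.191 = 0.16. With 1.5 SD, d² q = 2.25 × 0.250 = 0.562 and ρ = 0.562 / 1.562 = 0.36. With 41 patients (39 degrees of freedom, critical t = 2.02), two-sided significance needs |r| of about 2.02 / √(39 + 2.02²) = 0.31.

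**Simulated false significance.** Normal data, 21 + 20 patients, no within-arm relation, at least 20,000 replicates per row:

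| Shift on each variable (assumed) | ρ pooled | Pooled Pearson, p ≤ 0.05 | Adjusted for arm |
|---|---|---|---|
| 0 and 0 | 0.00 | 5% | 5% |
| 0.875 and 0 | 0.00 | 5% | 5% |
| 0.5 and 0.5 | 0.06 | 6–7% | 5% |
| 0.875–0.9 on both | 0.16–0.17 | about 18% | 5% |
| 1.2 and 1.2 | 0.26 | 40–41% | 5% |
| 0.875 and 1.5 | 0.24 | 34% | 5% |
| 1.5 and 1.5 | 0.36 | 68% | 5% |

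Pooled Spearman lies within 3 percentage points of Pearson throughout. Because CTCAE grades are ordinal, an assumed four-level outcome was also tried: it gave 17%, 39% and 67% at 0.9, 1.2 and 1.5 SD, and about 5% after adjustment. Neither ranks nor ties remove the problem; adjusting for arm does. If all 48 patients are evaluable, the pooled rate at 0.875 SD is 19.7%.

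**The case against.** The strongest reply is that the protocol never says the arms will be pooled or that markers will be correlated with outcomes. Correlations within each arm, or at baseline only, fit the same sentence and carry no arm effect. That stands: what is documented is an undefined analysis that permits the biased version, not a commitment to it.

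Four stronger readings are tempting, and the documents do not support them.

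- A reader might infer that a shared treatment effect will make the correlation significant. At 0.875 to 0.9 SD on both variables about 82% of pooled correlations are still non-significant. The artefact becomes more likely than not only above about 1.25 SD on both, and it vanishes if only one variable responds.
- A reader might take 0.9 SD as the design effect. The sample size rests on earlier studies of other drugs, and no effect size is given. The first-listed primary endpoint is a percentage, not a mean.
- Four markers and four clinical measures make 16 pairs, and 1 − 0.95^16 = 0.56, which suggests a 56% chance of some false positive. That needs all 16 tests to be run and to be independent. The protocol commits to no such set, and three of the four clinical measures assess the same neuropathy.
- A reader might think the trial's conclusions on efficacy are in doubt. No correlation is an endpoint, and the stated aim is a protective effect. The protocol does not claim that it will validate a marker.

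What remains is that the only stated method ignores arm, in a trial designed to move both variables, and that nothing in the protocol rules out pooling.

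**Conclusion.** The point holds in conditional form. If the arms are pooled and pentoxifylline shifts both variables of a pair, an unadjusted Pearson or Spearman test has a false-positive rate above its nominal 5%: slightly above it for moderate shifts, about 18% at the shift that 41 patients could detect with 80% power, and well over half at 1.5 SD. These figures assume equal within-arm variances, no within-arm relation and, except in the mixed rows of the table, equal shifts on both variables. The shifts themselves are illustrations, because the protocol supplies none. The harm is confined to biomarker and mechanism statements; the primary and secondary comparisons between arms are untouched. The matter is still worth correcting, because the remedy uses data already planned and costs almost nothing.

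**What to change.** Replace the correlation bullet in the Statistical analysis section with a sentence to this effect: associations between markers and clinical outcomes will be assessed by partial correlation (Pearson, or on ranks) of the change from baseline to after the last cycle, adjusted for treatment arm, or by correlations reported separately within each arm, for the listed pairs only, and will be labelled exploratory.

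Draw the list from the Introduction and the section on blood samples, for example: neurotensin and TNF-α each with BPI-SF worst pain and with Ntx-12; MDA with Ntx-12; citrulline with mucositis grade. That is six pairs. The interval from baseline to after the last cycle is the natural choice, because the markers are measured at those two times only.

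The cost is one sentence, one degree of freedom per correlation (38 instead of 39 with 41 patients) and fewer correlations to report. No new data, visits or patients are needed. Reporting within arms is equally free of the artefact but less precise, with only 20 or 21 patients in each.
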